**Table 2 Target Lesion Visit Responses**

Visit Responses	Description
Complete response (CR)	Disappearance of all TLs since baseline. Any pathological lymph nodes selected as TLs must have a reduction in short axis to <10 mm.
Partial response (PR)	At least a 30% decrease in the sum of the diameters of TL, taking as reference the baseline sum of diameters as long as criteria for PD are not met.
Stable disease (SD)	Neither sufficient shrinkage to qualify for PR nor sufficient increase to qualify for PD
Progression of disease (PD)	A $\geq 20\%$ increase in the sum of diameters of TLs and an absolute increase of $\geq 5\text{mm}$ , taking as reference the smallest sum of diameters since treatment started including the baseline sum of diameters.
Not evaluable (NE)	Only relevant in certain situations (ie, if any of the TLs were not assessed or not evaluable or had a lesion intervention at this visit; and scaling up could not be performed for lesions with interventions). Note: If the sum of diameters meets the progressive disease criteria, progressive disease overrides not evaluable as a TL response.
Not applicable (NA)	No TLs are recorded at baseline.

CR: Complete response; NA: Not applicable; NE: Not evaluable; PD: Progressive disease; PR: Partial response; SD: Stable Disease; TL: target lesion

### **Rounding of Target Lesion Data**

For calculation of PD and PR for TLs percentage changes from baseline and previous minimum should be rounded to 1 decimal place (dp) before assigning a target lesion response. For example, 19.95% should be rounded to 20.0% but 19.94% should be rounded to 19.9%

### **Missing TL Data**

For a visit to be evaluable then all target lesion measurements should be recorded. However, a visit response of PD should still be assigned if any of the following occurred

- A new lesion is recorded
- A NTL visit response of PD is recorded
- The sum of TLs is sufficiently increased to result in a 20% increase, and an absolute increase of  $\geq 5\text{mm}$ , from nadir even assuming the non-recorded TLs have disappeared

Note: the nadir can only be taken from assessments where all the TLs had a LD recorded.

If there is at least one TL measurement missing and a visit response of PD cannot be assigned, the visit response is NE.

If all TL measurements are missing, then the TL visit response is NE. Overall visit response

will also be NE, unless there is a progression of non-TLs or new lesions, in which case the response will be PD.

### **Lymph Nodes**

For lymph nodes, if the size reduces to  $< 10\text{mm}$  then these are considered non-pathological. However, a size will still be given, and this size should still be used to determine the TL visit response as normal. In the special case where all lymph nodes are  $< 10\text{mm}$  and all other TLs are  $0\text{mm}$  then although the sum may be  $>0\text{mm}$  the calculation of TL response should be over-written as a CR.

### **Target Lesion Visit Responses Subsequent to Complete Response**

A CR response can only be followed by CR, PD or NE. If a CR has occurred, then the following rules at the subsequent visits must be applied:

- Step 1: If all lesions meet the CR criteria (ie,  $0\text{mm}$  or  $< 10\text{mm}$  for lymph nodes) then response will be set to CR irrespective of whether the criteria for PD of TL is also met ie, if a lymph node LD increases by 20% but remains  $< 10\text{mm}$ .
- Step 2: If some lesion measurements are missing but all other lesions meet the CR criteria (ie,  $0\text{mm}$  or  $< 10\text{mm}$  for lymph nodes) then response will be set to NE irrespective of whether when referencing the sum of TL diameters, the criteria for PD is also met.
- Step 3: If not all lesions meet the CR criteria and the sum of lesions meets the criteria for PD then response will be set to PD
- Step 4: If after steps 1 – 3 a response can still not be determined the response will be set to remain as CR

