Baseline assessments should be performed no more than 28 days before the date of first IP administration, and ideally should be performed as close as possible to the date of first IP administration. Efficacy by RECIST 1.1 for all patients will be assessed according to the schedules of assessment. If an unscheduled assessment is performed, and the patient has not progressed, every attempt should be made to perform the subsequent assessments at their scheduled imaging visits.

Target lesions

Documentation of target lesions

A maximum of 5 measurable lesions, with a maximum of 2 lesions per organ (including lymph nodes collectively considered as a single organ), representative of all lesions involved should be identified as TL at baseline. TLs should be selected on the basis of their size (longest diameter for non-nodal lesions or short axis diameter for nodal lesions), but in addition should be those that lend themselves to reproducible repeated measurements. It may be the case that, on occasion, the largest lesion does not lend itself to reproducible measurement in which circumstance the next largest lesion, which can be measured reproducibly, should be selected.

The site and location of each TL should be documented as well as the longest diameter for non-nodal lesions (or short axis for lymph nodes). All measurements should be recorded in millimetres. At baseline the sum of the diameters for all TL will be calculated and reported as the baseline sum of diameters. At follow-up visits the sum of diameters for all TL will be calculated and reported as the follow-up sum of diameters.

Special cases:

- For TL measurable in 2 or 3 dimensions, always report the longest diameter. For pathological lymph nodes measurable in 2 or 3 dimensions, always report the short axis diameter.
- If the CT/MRI slice thickness used is >5 mm, the minimum size of measurable disease at baseline should be twice the slice thickness of the baseline scan.
- If a lesion has completely disappeared, the diameter should be recorded as 0 mm. If a lesion appears in the same location on a subsequent scan, it will be recorded as a NL.
- If a TL splits into 2 or more parts, then record the sum of the diameters of those parts.

- If 2 or more TLs merge then the sum of the diameters of the combined lesion should be recorded for one of the lesions and 0 mm recorded for the other lesion(s).

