#### 3.3.1 Progression-Free Survival

Progression-free survival is defined as the time from the date of first dose of durvalumab until the date of objective disease progression or death (by any cause in the absence of progression) regardless of whether the patient discontinues durvalumab or receives another anticancer therapy prior to progression.

- $PFS \text{ (days)} = (\text{date of PFS event or censoring}) - (\text{date of first dose of durvalumab}) + 1.$

Patients who have not progressed or died at the time of analysis will be censored at the date of their last evaluable tumour assessment (ie, this doesn't include NE or missing value).

If the patient progresses or dies after 2 or more missed visits, the patient will be censored at the date of the latest evaluable RECIST 1.1 assessment prior to the two missed visits.

Given the scheduled visit assessment scheme (i.e. eight-weekly for the first 48 weeks then twelve-weekly thereafter) the definition of 2 missed visits will change.

1. If the previous RECIST assessment is baseline then two missing visits will equate to 17 weeks since the previous RECIST assessment, allowing for a late visit (i.e.  $2 \times 8 \text{ weeks} + 1 \text{ week for a late assessment} = 17 \text{ weeks}$ ).
2. If the previous RECIST assessment is post baseline and less than study day 274 (i.e. week 39) then two missing visits will equate to 18 weeks since the previous RECIST assessment, allowing for early and late visits (i.e.  $2 \times 8 \text{ weeks} + 1 \text{ week for an early assessment} + 1 \text{ week for a late assessment} = 18 \text{ weeks}$ ).
3. If the two missed visits occur over the period when the scheduled frequency of RECIST assessments changes from eight-weekly to twelve-weekly this will equate to 22 weeks (i.e. take the average of 8 and 12 weeks which gives 10 weeks and then apply same rationale, hence  $2 \times 10 \text{ weeks} + 1 \text{ week for an early assessment} + 1 \text{ week for a late assessment} = 22 \text{ weeks}$ ). The time period for the previous RECIST assessment will be from study days 274 to 344 (i.e. week 39 to week 49).
4. From week 49 onwards (when the scheduling changes to twelve-weekly assessments), two missing visits will equate to 26 weeks (i.e.  $2 \times 12 \text{ weeks} + 1 \text{ week for an early assessment} + 1 \text{ week for a late assessment} = 26 \text{ weeks}$ ).

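### After a target-lesion CR, a visit with one target lesion unmeasured and another regrown below PD is set to CR by Step 4, although the SAP's missing-data rule sets it to NE

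*SAP*

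**What the plan says.** SAP 3.1.1.1, under the heading on TL responses subsequent to a complete response, limits what may follow: "A CR response can only be followed by CR, PD or NE". It then makes four steps mandatory at later visits.

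- Step 1: every TL meets the CR criteria (0 mm, or under 10 mm for a node). The response is CR, even if the sum would meet PD.
- Step 2: "If some lesion measurements are missing but all other lesions meet the CR criteria". The response is NE, even if the sum would meet PD.
- Step 3: "not all lesions meet the CR criteria and the sum of lesions meets the criteria for PD". The response is PD.
- Step 4: if Steps 1 to 3 give no answer, "a response can still not be determined the response will be set to remain as CR".

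Earlier in the same section, under Missing TL Data, the general rules are: "If there is at least one TL measurement missing and a visit response of PD cannot be assigned, the visit response is NE", and "If all TL measurements are missing, then the TL visit response is NE". Neither passage refers to the other, and the SAP does not say which governs after a CR.

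**The concern.** One kind of visit falls between the steps. At least one TL is unmeasured, a measured TL no longer meets CR, and the partial sum is below PD. It fails Step 1 because not every TL meets CR, Step 2 because a measured TL fails CR, and Step 3 because the sum is below PD. Step 4 therefore makes it CR, while Missing TL Data makes it NE. Two programmers working from the same SAP could derive different responses.

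The label matters because CR is evaluable and NE is not. Under SAP Table 4, a TL CR gives an overall CR, or an overall PR if non-target disease persists or is not evaluable. Either one counts as a response. The visit can then act as the repeat scan at four weeks or more that confirms response for ORR, best objective response and DoR (SAP 3.3.3 to 3.3.5). It also enters PFS, where "Patients who have not progressed or died at the time of analysis will be censored at the date of their last evaluable tumour assessment", and DoR takes its end date from PFS. It restarts the count behind the two-missed-visits rule in SAP 3.3.1.

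**Working it through.** The plan states no figure for this rule, so the check applies the steps as written.

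**Inputs**

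- CR: a non-nodal TL at 0 mm, a node under 10 mm in short axis (SAP Table 2 and Lymph Nodes).
- PD: the sum is up by at least 20% and at least 5 mm from the nadir (SAP Table 2). With a TL missing, PD is assigned only if the partial sum is large enough with the missing TL counted as 0 mm (Missing TL Data).
- At most two nodal TLs (protocol Appendix F).
- Assumed example: two nodes of 9 mm each at CR, and this sum is the nadir, N = 9 + 9 = 18 mm.

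**Formula.** With partial sum S, the increase is S − N mm, or 100 × (S − N)/N percent. At N = 18, 5 mm is 27.8% of the nadir, so the 5 mm condition decides.

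| Next visit | S − N | Percent | Post-CR steps | Missing TL Data |
|---|---|---|---|---|
| 9 mm, missing | −9 mm | −50.0 | Step 2: NE | NE |
| 20 mm, missing | +2 mm | +11.1 | Step 4: CR | NE |
| 22 mm, missing | +4 mm | +22.2 | Step 4: CR | NE |
| 23 mm, missing | +5 mm | +27.8 | Step 3: PD | PD |

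In whole millimetres, a measured node from 10 to 22 mm gives CR, yet one of 9 mm gives NE. More disease earns the better label. A 22 mm node is above both the 10 mm limit for CR and the 15 mm short axis that makes a node measurable.

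**Enumeration.** Take two nodes, each 0 to 9 mm at CR, with the next visit at 0 to 30 mm and exactly one node missing. That gives 10 × 10 × 31 × 2 = 6,200 combinations: 2,000 are NE at Step 2, 3,330 are PD at Step 3, and 870 are CR at Step 4. Missing TL Data would make all 870 NE. The largest growth of the measured node among them is 22 − 9 = 13 mm. These are counts of combinations, not of patients.

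**Effect on ORR.** One wrongly confirmed responder adds 1/30 = 3.3 points in a PS 2 cohort of 30, and 1/130 = 0.8 points overall if 100 + 30 patients are treated.

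**Effect on PFS and DoR**, assuming an NE visit does not count as the previous assessment in the two-missed-visits rule:

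- No later event. The last evaluable scan is week 16 and the disputed visit is week 24. Censoring is at week 16 under NE and week 24 under CR, 8 weeks later. On the later schedule the shift is 12 weeks.
- Later PD. Same visits, then week 32 missed and PD at week 40. Under NE the gap is 40 − 16 = 24 weeks, beyond the 18-week limit, so the patient is censored at week 16. Under CR the gap is 40 − 24 = 16 weeks, so the PD counts as an event.

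The first case lengthens follow-up without an event. The second adds an event.

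**The case against.** The best defence is that Missing TL Data is a general rule which already determines the response, so Step 4, a default for undetermined visits, is never reached. That reading is possible. But Step 4 makes its test the failure of Steps 1 to 3, the steps are mandatory after a CR, and Step 2 handles missing measurements inside the same list. The specific text can fairly be taken to govern, and nothing in the SAP rules that out.

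The defence is right that the effect is small. The endpoints are secondary and descriptive, with no hypothesis test. An NE visit does not end the chance of confirmation at a later scan, so ORR changes only if the disputed visit is the sole confirming scan.

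A reader might infer more than the documents support:

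- That visits with every TL unmeasured become CR. Step 2 speaks only of some lesions missing, but "If all TL measurements are missing, then the TL visit response is NE" settles the case directly.
- That a reappearing non-nodal TL stays CR. Protocol Appendix F says of a lesion that had disappeared: "If a lesion appears in the same location on a subsequent scan, it will be recorded as a NL". Under SAP 3.1.1.2 a new lesion makes the overall response PD. What remains is that the SAP's TL section does not repeat this rule. A regrowth from 0 to 4 mm entered as a TL size, with no new lesion ticked, would get a TL response of CR.
- That fully measured nodal regrowth is misclassified. Nodes of 9 + 9 mm going to 13 + 9 mm (+4 mm, +22.2%) do reach Step 4. But in whole millimetres the sum can rise by at most 4 mm there, and the documents do not say such growth is PD.
- That every such error favours the drug. The second PFS case above goes the other way, and no visit meeting PD criteria is lost, since Step 3, non-target PD and new lesions still apply.

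**Conclusion.** The point holds for one class of visit: after a TL CR, at least one TL missing, a measured TL no longer meeting CR, and a partial sum below PD. There the SAP contains two conflicting rules, and the more specific one gives an implausible and evaluable CR. The size per patient is as shown above: up to one wrongly confirmed responder, or a shift of a scan interval in censoring, with no uniform direction of bias. The documents give no rate of CR or of missing lesion measurements, so the number of patients cannot be calculated; it is likely to be few. The primary endpoint, Grade 3 and 4 treatment-related events, is untouched. The examples assume that the sum at CR is the nadir and that sizes are in whole millimetres. The correction is worth making because it is cheap and removes an ambiguity in programming.

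**What to change.** Keep Steps 1 to 3 as written, including Step 2's NE regardless of the sum. Replacing Step 2 with a rule that gives NE only when PD cannot be assigned would create a new error. With nodes of 2 + 2 mm at the nadir and then 9 mm and missing, the sum rises 9 − 4 = 5 mm (+125%), so the visit would become PD although the only measured node is still under 10 mm.

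Then make three changes:

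1. Before Step 4, insert: if any TL measurement (some or all) is missing and Step 3 has not assigned PD, the response is NE, as under Missing TL Data. Lesions treated as missing because of an on-study intervention stay under the SAP's own intervention and scaling rules.
2. Limit Step 4 to visits where every TL is measured.
3. Add a cross-reference to protocol Appendix F, so that a non-nodal TL reappearing after 0 mm is handled as a new lesion, with an overall response of PD.

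The cost is SAP wording and a small change to the response derivation program. No new data are needed. ORR may become slightly less favourable.

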### **Target Lesion Too Big to Measure**

If a target lesion becomes too big to measure this should be indicated in the database and a size ('x') above which it cannot be accurately measured should be recorded. If using a value of x in the calculation of target lesion response would not give an overall visit response of PD, then this will be flagged and reviewed by the study team. It is expected that a visit response of PD will remain in the vast majority of cases.

### **Target Lesion Too Small to Measure**

If a TL becomes too small to measure, then this will be indicated as such on the case report form and a value of  $5\text{mm}$  will be entered into the database and used in TL calculations. However, a smaller value may be used if the radiologist has not indicated 'too small to measure' on the case report form and has entered a smaller value that can be reliably measured. If a TL response of PD results, then this will be reviewed by the study team.

### **Irradiated Lesions/Lesion Intervention**

A previously irradiated lesion may be selected as a TL, provided that it fulfils the criteria for reproducible measurability and is the only lesion available.

Any TL (including lymph nodes), which has had intervention in addition to study treatment during the study (eg, irradiation / palliative surgery / embolization), should be handled in the

following way and once a lesion has had intervention then it should be treated as having intervention for the remainder of the study noting that an intervention will most likely shrink the size of tumours:

- Step 1: the diameters of the TLs (including the lesions that have had intervention) will be summed and the calculation will be performed in the usual manner. If the visit response is PD this will remain as a valid response category.
- Step 2: If there was no evidence of progression after step 1, treat the lesion diameter (for those lesions with intervention) as missing and if  $\leq 1/3$  of the TLs have missing measurements then scale up as described in the 'Scaling' section below. If the scaling results in a visit response of PD then the patient would be assigned a TL response of PD.
- Step 3: If, after both steps, PD has not been assigned, then, if appropriate (ie, if  $\leq 1/3$  of the TLs have missing measurements), the scaled sum of diameters calculated in step 2 should be used, and PR or SD then assigned as the visit response. Patients with intervention are evaluable for CR as long as all non-intervened lesions are 0 (or <10mm for lymph nodes) and the lesions that have been subject to intervention have a value of 0 (or <10mm for lymph nodes) recorded. If scaling up is not appropriate due to too few non-missing measurements, then the visit response will be set as NE.

At subsequent visits the above steps will be repeated to determine the TL and overall visit response. When calculating the previous minimum, lesions with intervention should be treated as missing and scaled up (as per step 2 above).

### **Scaling of the Sum of Target Lesions**

Scaling of the sum of target lesion diameters is used when one or more target lesion diameter is missing because of on-study target lesion intervention.

If more than one third of target lesion measurements are missing (because of intervention) then target lesion response will be NE, unless the sum of diameters of non-missing target lesion would result in PD (ie, if using a value of 0 for missing lesions, the sum of diameters has still increased by > 20% or more compared to nadir and the sum of target lesions has increased by  $\geq 5$ mm from nadir).

If  $\leq 1/3$  of the target lesion measurements are missing (because of intervention) then the results will be scaled up based on the sizes at the nadir visit to give an estimated sum of diameters and this will be used in calculations; this is equivalent to comparing the visit sum of diameters of the non-missing lesions to the nadir sum of diameters excluding the lesions with missing measurements.

## Example of Scaling

Lesion	Longest diameter (mm) at nadir visit	Longest diameter (mm) at follow-up visit
1	16	18
2	14	16
3	14	16
4	18	18
5	12	Intervention
Sum	74	68

Lesion 5 has had an intervention at the follow-up visit. The sum of the Baseline measures is 74 mm. The sum of lesions 1-4 at the follow-up is 68 mm. The sum of the corresponding lesions at nadir visit is 62 mm. Scale up as follows to give an estimated follow-up visit TL sum of 81mm:

$$\frac{68}{62} \times 74 = 81mm$$

### Lesions that Split in Two or more Parts

If a TL splits in two or more parts, then the LDs of the split lesions should be summed and reported as the LD for the lesion that split.

### Lesions that Merge

If two or more target lesions merge, then the LD of the merged lesion should be recorded for one of the TL sizes and the other TL sizes should be recorded as 0mm.

### Change in Method of Assessment of Target Lesions

CT and MRI are the only methods of assessment that can be used within this trial. If a change in method of assessment between CT and MRI occurs this will be considered acceptable and no adjustment within the programming is needed.

Note, if a change in method involves clinical examination (eg, CT changes to clinical examination or vice versa), any affected lesions should be treated as missing.

#### 3.1.1.2 Non-Target Lesions and New Lesions.

At each visit an overall assessment of the NTL response should be recorded by the investigator. This section provides the definitions of the criteria used to determine and record overall response for NTL at the investigational site at each visit.

Non-target lesion response will be derived based on the Investigator's overall assessment of NTLs as follows:

**Table 3 NTL Visit Responses**

Visit Responses	Description
Complete response (CR)	Disappearance of all NTLs since baseline. All lymph nodes must be non-pathological in size (<10 mm short axis).
Non CR/non PD Progression (PD)	Persistence of one or more NTLs with no evidence of progression. Unequivocal progression of existing NTLs. Unequivocal progression may be due to an important progression in one lesion only or in several lesions. In all cases the progression MUST be clinically significant for the physician to consider changing (or stopping) therapy.
Not evaluable (NE)	Only relevant when one or some of the NTLs were not assessed and, in the Investigator's opinion, they are not able to provide an evaluable overall NTL assessment at this visit.  Note: for patients without TLs at baseline, this is relevant if any of the NTLs were not assessed at this visit and the progression criteria have not been met.
Not applicable (NA)	Only relevant if there are no NTLs at baseline.

CR: Complete response; NA: Not applicable; NE: Not evaluable; NTL non-target lesion; PD: Progressive disease; PR: Partial response; SD: Stable Disease; TL: target lesion

To achieve 'unequivocal progression' based on NTLs, there must be an overall level of substantial worsening in non-target disease such that, even in the presence of SD or PR in TLs, the overall tumour burden has increased sufficiently to merit a discontinuation of therapy. A modest 'increase' in the size of one or more NTLs is usually not sufficient to qualify for unequivocal progression status.

Details of any new lesions will also be recorded with the date of assessment. The presence of one or more new lesions is assessed as progression.

A lesion identified at a follow up assessment in an anatomical location that was not scanned at baseline is considered a new lesion and will indicate disease progression.

The finding of a new lesion should be unequivocal: ie, not attributable to differences in scanning technique, change in imaging modality or findings thought to represent something other than tumour.

New lesions will be identified via a Yes/No tick box. The absence and presence of new lesions at each visit should be listed alongside the TL and NTL visit responses.

A new lesion indicates progression, so the overall visit response will be PD irrespective of the TL and NTL response.

Symptomatic deterioration is not a descriptor for progression of NTLs: it is a reason for stopping study therapy and will not be included in any assessment of NTLs.

Patients with 'symptomatic deterioration' requiring discontinuation of treatment without objective evidence of disease progression at that time should continue to undergo tumour

assessments where possible until objective disease progression is observed.

